5. STUDY DRUG, CONCOMITANT THERAPY AND LIFE-STYLE CONSIDERATIONS

Study drug is defined as investigational drug (VXA-CoV2-1.1-S), or placebo, intended to be administered to a study participant according to the study protocol.

5.1. Study Drug Administration

VXA-CoV2-1.1-S is an E1/E3-deleted, replication-incompetent, adenovirus 5 vaccine vector designed for use as an oral vaccine. The vaccine vector encodes the full-length Spike protein (S) of SARS-COV-2 specific antigen. The adjuvant consists of a double-stranded RNA Toll-like receptor 3 (TLR3) agonist which enhances immune induction to expressed antigen in the gut mucosa.

Intervention Name	VXA-CoV2-1.1-S (Part 1 and Part 2)	Placebo (Part 2 only)		
Туре	biologic	Matching placebo		
Dose Formulation	enteric-coated tablets	enteric-coated tablets		
Unit Dose Strength(s)	The target concentration of drug product (DP) per tablet will vary per manufacturing lot (e.g. $5x10^9$ to $1.7x10^{10}$ International Units [IU] each). Multiple tablets may be dispensed to deliver the target dose.			
Dosage Level(s)	Low dose: $1x10^{10}$ IU ± 0.5 log High dose: $1x10^{11}$ IU ± 0.5 log	Matching placebo tablets in appearance and number of tablets administered.		
	The number of tablets per dose will be determined based on potency assay during release testing of each DP tablet lot. Multiple tablets may be administered to constitute the full dose. Dosing instructions will be described in detail within the Pharmacy Manual.			
Route of Administration	Oral			
Administration instructions	Participants should fast and refrain from ingesting solid food for at least 4 hours prior to oral dosing. A trained member of the site study staff will dispense the tablet(s) constituting the assigned dose to the participant. The participants will swallow the tablets with 360 to 480 mL of water followed by a light snack (e.g., crackers) at time of dosage administration to aid in tablet transit out of the stomach. Normal food consumption may resume 90 minutes after dosing. For more information refer to the Study Pharmacy Manual.			
Sourcing	Study drug will be provided to the site centrally by the Sponsor or designated representative.			
Packaging and Labeling	The tablets are packaged in foil-sealed, high-density polyethylene (HDPE) screw-cap containers with 10 tablets per bottle. All packaging and labeling operations for study drug will be performed			
	according to Good Manufacturing Practi			

Table 4Study Drug

Intervention Name	VXA-CoV2-1.1-S (Part 1 and Part 2)	Placebo (Part 2 only)		
	Products and the relevant regulatory requirements. Label text for the study drug bottle will at a minimum include name of the manufacturer, the protocol number, the name of the product, the lot number of the product, the concentration of the vaccine, and the date of manufacturing or expiration.			
	Secondary packaging of the study drug upon dispensing from the pharmacy to the clinical staff for participant dosing will be determined with consideration of the sites' pharmacy standard operating procedures and outlined in the study pharmacy manual.			
	The final dispensing container (cup or secondary bottle) will be appropriately labeled with the participant's unique identifier, the time/date of dose preparation within the pharmacy and additional information as deemed necessary per the site's Standard Operating Procedures (SOPs).			
Storage Condition	VXA-CoV2-1.1-S vaccine tablets will be clinical site until ready for use. Tablets s use and contact Sponsor if DP tablets ha	hould not be frozen . Do not		

5.2. Compliance of Study drug

Participants will receive study drug directly from the Investigator or designee, under medical supervision. The date and time of each dose administered in the clinic will be recorded in the source documents and recorded in the electronic Case Report Form (eCRF). The dose of study drug and study participant identification will be confirmed at the time of dosing by a member of the study site staff other than the person administering the study drug.

5.2.1. Dose Adjustments/Modifications/Delays

Dose adjustments and or modifications are not planned or allowed under this clinical protocol. All participants should receive the full dose they are assigned to, either the low dose $(1x10^{10} \text{ IU} \pm 0.5 \text{ log})$ or the high dose $(1x10^{11} \text{ IU} \pm 0.5 \text{ log})$ at the protocol-defined study visits (Day 1 and Week 4) after meeting eligibility. Any modification from this schedule or planned dose should be recorded as a protocol violation and reported to the Sponsor (or designee).

5.3. Handling and Accountability

- 1. The Investigator or designee must confirm appropriate temperature conditions have been maintained during transit for study drug received and any discrepancies are reported and resolved before use of study drug.
- 2. Only participants enrolled in the study may receive study drug and only authorized site staff may supply or administer study drug. All study drug must be stored in a secure, environmentally controlled, and monitored (manual or automated) area in accordance with the labeled storage conditions with access limited to the Investigator and authorized site staff.
- 3. The Investigator, institution, or the head of the medical institution (where applicable) is responsible for study drug accountability, reconciliation, and record maintenance (i.e., receipt, reconciliation, and final disposition records).

4. At the end of the study, the monitor will conduct a final drug reconciliation for all participants and the study site overall. All records of study drug administration, accountability records and study drug disposition records will be examined and reconciled by the study monitor. Further details will be provided in the Study Pharmacy Manual.

Further guidance and information for the final disposition of unused study drug are provided in the Pharmacy Manual.

5.4. Measures to Minimize Bias: Randomization and Blinding

5.4.1. Assignment of a Participant Number

Each participant who signs informed consent will be assigned a participant number. This number will be used as the primary identification for the complete duration of the study. After the participant has signed the informed consent form (ICF), the Investigator will enter the participant into the Screening section of the electronic case report form (eCRF).

5.4.2. Randomization (Part 2 only)

Participants in Part 2 will be randomized in a 1:1 ratio to receive VXA-CoV2-1.1-S (at dose selected from Part 1 of the study) or matching placebo.

Randomization will be centralized across all study sites by region using the Randomization and Trial Supply Management (RTSM) system.

Randomization will be stratified by age (18 - 55 years and 56 - 75 years) and region (if sites in multiple countries are utilized).

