Treatment Arms	Treatment*	Treatment Timepoints	No. of Participants**
Active	Oral tableted VXA-CoV2-1.1-S vaccine (Dose to be selected after Part 1 data review)	Day 1 & Week 4	400
Control	Matching oral placebo tablet(s)	Day 1 & Week 4	400

* Multiple tablets may be administered to deliver the full intended dose.

** A minimum of 200 participants (25%) in Part 2 will be >55 years old.

Duration of Study Participation

For each participant in Part 2 the duration of study activities is expected to last as follows:

Study Period (Part 2)	Duration
Screening Period:	30 days
Active Period:	8 weeks*
Efficacy Evaluation:	~6 months (starting 7 days after second dose)
Safety Follow-up Period:	11 months
Total duration of participation:	~14 months

* Participants who discontinue study drug early will enter the Safety Follow-up Period at Week 4.

**The study database will be cleaned and locked following completion of the efficacy period. Treatment assignments for Part 2 will be unblinded following completion of the primary efficacy analyses.

Scheduled Study Visits

Study Period	Part 1 and Part 2 Site Visits						
Screening	Day -30 to Day -1						
	Week 0 (Day 1) – First dose administration						
	Week 1 (Day 8)						
Active	Week 4 (Day 29) – Second dose administration						
	Week 5 (Day 36)						
	Week 8 (Day 57) – End of Study Active Period Visit						
	Months 3, 4, 5, 6, 8, 9, 10, 11 and 12 (phone calls)						
Safety Follow-up	Month 7						
	Month 13 – End of Study Visit						

Study Sites

Part 1: 4 to 8 qualified clinical sites in the United States (U.S.).

Part 2: 30 to 60 qualified clinical sites in the U.S., Latin America, South Africa and/or India, as required to complete study enrollment.

Independent Data Monitoring Committee (IDMC):

Refer to Section 8.5.2 for information on IDMC scheduled meetings for Part 1 and study oversight for Parts 1 and 2.

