8. STATISTICAL CONSIDERATIONS

8.1. Sample Size Determination

8.1.1. Part 1

Part 1 is an open-label, lead in, repeat-dose, dose and age escalation design to evaluate the VXA-COV2-1.1-S oral vaccine in two cohorts with repeat dose administration. Cohort 1 will enroll approximately a total of 36 healthy adult participants that are naive (no prior vaccination against SARS-CoV-2 infection and no history of prior COVID-19 or SARS-CoV-2 infection) across 3 groups of 12 subjects each, encompassing 2 age groups and two dose levels. Cohort 2 will enroll approximately a total of 36 healthy adult participants who have received two doses of an EUA or FDA approved mRNA vaccine for the prevention of SARS-CoV-2 infection across 3 groups of 12 subjects each, encompassing 2 age groups and two dose levels.

There are no sample size calculations utilized for Part 1; the cohort size is estimated to provide informative safety and immunogenicity data to allow dose selection for safely proceeding to Part 2.

8.1.2. Part 2

The number of participants to be randomized in Part 2 (VXA-CoV2-1.1-S and placebo) is predicted to yield meaningful immunogenicity and efficacy results to inform how best to proceed into later stage studies. In previous human studies with Ad5 vectored oral tableted vaccines using the same vaccine platform (Ad5 vectored vaccine coding for target virus-specific antigens and a dsDNA adjuvant), the vaccine was well tolerated at total doses up to $2x10^{11}$ IU.

All testing will be performed at alpha = 0.05. All tests will be two-sided. Assuming attack rate in unvaccinated group (ARU) = 5% and vaccine efficacy (VE) = 90%, 341 participants would be required per treatment arm, yielding 95% power.

The total sample size for Part 2 of this study (2 arms) would be 682. To allow for a $\sim 15\%$ dropout rate, 800 participants will be randomized.

2-sided Alpha	0.05	0.05	0.05	0.05	0.05	0.05	0.05	0.05
ARU	5%	5%	5%	5%	5%	5%	5%	5%
VE	90%	90%	90%	90%	95%	95%	95%	95%
Power	80%	85%	90%	95%	80%	85%	90%	95%
SS/Arm	207	236	276	341	177	202	236	292
Sample Size (part 2 of								
study, two arms)	414		472	682	354	404	472	584

Unvaccinated Atta	ck Rate (ARU): 5%
--------------------------	-------------------

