8.3.2. Part 2- Double Blind, Placebo Controlled

Endpoint	Statistical Analysis Methods
Primary: 1. Primary Efficacy	All analyses will be performed at 6 months post last vaccination. The database will be locked and unblinded at this time the efficacy and safety analysis will be conducted.
2. Secondary Efficacy	The evaluable efficacy population will be the primary analysis population for all efficacy analyses. Additional analyses based on the all-available efficacy population will be performed.
3. Safety	1. Primary Efficacy
	Frequency of virologically confirmed COVID-19 illness and serologically confirmed SARS-CoV-2 infection occurring from 7 days following second study drug dose administration.
	Ratio of confirmed COVID-19 illness from 1 week after the Dose 2 per 1000 person-years of follow-up in participants without evidence of infection for the active vaccine group to the placebo group VE will be estimated by $100 \times (1 - IRR)$, where IRR is the calculated ratio of confirmed COVID-19 illness per 1000 person-years follow-up in the active vaccine group to the corresponding illness rate in the placebo group from 1 week after the Dose 2.
	VE will be analyzed using a beta-binomial model. After the above objective is met, the second primary endpoint will be evaluated as below. Ratio of confirmed COVID-19 illness from 1 week after the Dose 2 per 1000 person-years of follow-up in participants with and without evidence of infection (prior to 1 week after

Vaxart,	Inc.
---------	------

receipt of Dose 2) for the active vaccine group to the placebo group VE will be estimated by $100 \times (1 - IRR)$, where IRR is the calculated ratio of confirmed COVID-19 illness per 1000 person-years follow-up in the active vaccine group to the corresponding illness rate in the placebo group from 1 week after the second dose. VE will be analyzed using a beta-binomial model.
The efficacy analysis for the first primary objective evaluation will be based on the participants without evidence of infection before vaccination and included in the evaluable efficacy population and in the all-available efficacy population.
The efficacy analysis for the second primary objective evaluation will be based on all participants included in the evaluable efficacy population and in the all- available efficacy population.

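### Part 2 randomization is stratified by age and, if used, region, but the primary vaccine efficacy is a pooled rate ratio, open to bias if post-randomization losses differ by arm across strata

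*Combined protocol and SAP*

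**What the plan says.** On design, section 5.4.2 states: "Participants in Part 2 will be randomized in a 1:1 ratio". It then adds: "Randomization will be stratified by age (18 - 55 years and 56 - 75 years) and region", with region applying only if more than one country takes part; section 4.2 says the same. The synopsis foresees "30 to 60 qualified clinical sites in the U.S., Latin America, South Africa and/or India" for Part 2, as enrollment requires. Age is therefore always a stratum, and region is a conditional one.

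On analysis, section 8.3.2 takes VE, in percent, as one minus an incidence rate ratio (IRR). It defines that ratio in these words: "where IRR is the calculated ratio of confirmed COVID-19 illness per 1000 person-years follow-up in the active vaccine group to the corresponding illness rate". The comparator is placebo. For each of the two primary analyses it adds: "VE will be analyzed using a beta-binomial model". No efficacy analysis in 8.3.2 names age group or region as a stratum or covariate.

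The main efficacy population is defined after randomization. Section 8.2 requires all doses as randomized, within the window, and no other important protocol deviation. The first primary analysis also drops participants with evidence of infection. Section 4.2.2 withholds dose 2 after certain adverse events, acute illness or a positive pregnancy test. Section 8.1.2 allows for about 15% dropout.

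**The concern.** A pooled rate ratio adds cases and person-time over strata before dividing. It equals the common within-stratum ratio when the two arms spread their person-time over the strata in the same proportions. Stratified 1:1 randomization secures this for the number of people at Day 1. It does not secure it for person-time after losses and exclusions.

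Dose-2 ineligibility for treatment-related events could fall more on vaccine recipients, and acute illness could follow local incidence. If such losses differ by arm in some strata and not in others, and attack rates differ between those strata, the pooled VE moves away from the true value in either direction. At stake is a modest error in the primary estimate, and a choice between pooled and stratified results that 8.3.2 does not settle in advance.

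**Working it through.** **The plan's own figure.** Section 8.1.2 says: "Assuming attack rate in unvaccinated group (ARU) = 5% and vaccine efficacy (VE) = 90%, 341 participants would be required per treatment arm", at 95% power and two-sided alpha 0.05. The attack rates are 0.05 and 0.05 × (1 − 0.90) = 0.005, with mean 0.0275.

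n = [1.960 × √(2 × 0.0275 × 0.9725) + 1.645 × √(0.05 × 0.95 + 0.005 × 0.995)]² / 0.045² = 340.3, so 341 per arm. This reproduces. The calculation is unstratified; nothing below changes it.

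**Formulas.** Let r be the placebo rate in a stratum, and T1 and T0 the vaccine and placebo person-time there. With a common true VE:

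- Pooled IRR = (1 − VE) × [Σ r·T1 / Σ T1] / [Σ r·T0 / Σ T0]
- Mantel-Haenszel IRR = [Σ r(1 − VE)·T1·T0/(T1+T0)] / [Σ r·T0·T1/(T1+T0)] = 1 − VE, whatever T1 and T0 are

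**Inputs.** The 1:1 allocation is from 5.4.2. Regional attack rates and losses are not in the documents. I assume three equal regions with r = 2, 5 and 10 (percent), and T = 1 unless stated.

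**Cases without bias.**

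- Follow-up doubled in the highest-rate region in both arms: both brackets are (2 + 5 + 20)/4, so the pooled IRR is exactly 1 − VE.
- Placebo person-time 20% shorter in every region: 13.6/2.4 = 17/3, so again exactly 1 − VE. A person-time ratio that is constant over strata does no harm.

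**A small residual.** If participants leave the risk set at their first case, placebo person-time shrinks slightly faster where rates are high. For true VE of 30% to 90%, the pooled estimate falls short by these amounts under assumed 6-month attack rates:

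- 2% and 8% (6 and 12 months' follow-up): 0.1 to 0.4 points
- four regions at 1%, 3%, 6% and 12% (6 to 12 months): 0.3 to 0.8 points
- 1% and 15% (6 and 12 months): 0.4 to 1.2 points
- 1% and 30% (6 and 12 months): 1.1 to 3.1 points

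It is zero when true VE is 0.

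**Case with bias: person-time shorter in one arm, in the highest-rate region only.**

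- Placebo 20% shorter: vaccine bracket 17/3 = 5.667; placebo bracket (2 + 5 + 8)/2.8 = 5.357; factor 1.058.
- Placebo 7.5% shorter: placebo bracket (2 + 5 + 9.25)/2.925 = 5.556; factor 1.020.
- Vaccine 20% shorter: factor 5.357/5.667 = 0.945.

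Pooled VE = 1 − factor × (1 − true VE):

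| True VE | Placebo −7.5% | Placebo −20% | Vaccine −20% | Stratified |
|---|---|---|---|---|
| 90% | 89.8% | 89.4% | 90.5% | 90% |
| 80% | 79.6% | 78.8% | 81.1% | 80% |
| 50% | 49.0% | 47.1% | 52.7% | 50% |
| 30% | 28.6% | 26.0% | 33.8% | 30% |
| 0% | −2.0% | −5.8% | 5.5% | 0% |

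The 7.5% figure is what 15% dropout costs if it is spread evenly over follow-up (0.15 × ½) and falls wholly on placebo in that region. A 20% deficit would need about 40% excess dropout there.

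**Scale against chance.** Section 8.4 expects about 5 vaccine and 26 placebo cases. The standard error of log IRR is then about √(1/5 + 1/26) = 0.49. The shifts are ln 1.020 = 0.020 and ln 1.058 = 0.056, or about 4% and 12% of one standard error.

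**Cost in precision.** I simulated 400 per arm, the rates above and 15% loss equal in both arms. The standard deviation of log IRR, pooled against Mantel-Haenszel, was 0.580 against 0.581 at VE 80%, 0.348 against 0.350 at 30%, and 0.318 against 0.321 at 0%. These differences are below 1%.

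**The case against.** A reader might infer that pooling over regions with different attack rates and follow-up biases VE in itself. The documents do not support that: allocation is 1:1 within strata, the weights cancel, and only the small depletion residual remains.

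The best case for leaving 8.3.2 alone is that the required imbalance is speculative. Part 2 is double-blind with matching placebo, and placebo participants are offered vaccination only after unblinding at the end of the Efficacy Period. The 20% scenario is extreme. At the design VE of 90% even that scenario moves VE by 0.6 points, well inside sampling error. If placebo loses the time, the error runs against the vaccine. All of this stands, and it limits the size. It does not rule out losses that fall on the vaccine arm, which would flatter the vaccine, nor exclusions under 8.2, which randomization does not control.

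Three further points stand:

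- Region is a stratum only if several countries are used. In a single-country trial only age remains, and the regional figures above say nothing about age.
- Stratifying corrects imbalance between strata. It does not correct informative dropout within a stratum.
- Section 8.3 defers detail to an SAP to be finalized before database lock, and its text is not in the supplied document. A reader should not conclude that a stratified analysis is absent from it. The point concerns 8.3.2, which already fixes a pooled estimator.

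**Conclusion.** The mismatch between stratified randomization and a pooled primary estimator in 8.3.2 is real. It leaves the estimate exposed to bias only if the vaccine:placebo person-time ratio comes to differ between strata with different attack rates.

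Under the assumed regional rates and a 7.5% to 20% placebo deficit in one region, the downward shift is 0.2 to 0.6 points at true VE 90% and 1.4 to 4.0 points at 30%. A 20% vaccine deficit shifts VE upward by about 0.5 and 3.8 points respectively. These figures rest on assumed rates and losses and on a common VE across strata. If VE differs by region, the question becomes which average is wanted.

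Nothing here shows that the planned analysis will be biased, and the sample size is unaffected. The change is worth making because it removes this route to bias at almost no cost in precision.

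**What to change.** In 8.3.2, estimate VE for both primary analyses from the person-time rate ratio stratified by age group and, where several countries take part, region. Use Mantel-Haenszel, or an exact conditional analysis stratified the same way. Strata without cases contribute nothing, so sparse strata are no obstacle. Keep the pooled beta-binomial estimate as a prespecified sensitivity analysis; this preserves the link to the unstratified case split used for event planning in 8.4.

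Carry the same wording into the SAP before unblinding. Report person-time and exclusions by arm within stratum, so that any imbalance is visible and dropout within strata can be judged separately.

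The cost is wording in the protocol and SAP. No extra data or participants are needed.

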5.4.3. Blinding and Unblinding (Part 2 only)

Participants, Investigators, site personnel and the Sponsor (except as described below) will be blinded to individual participant treatment assignment in Part 2.

Study drug doses will be prepared at the study sites by an unblinded research pharmacist(s) who will be provided treatment assignment through a RTSM System.

Sponsor representative(s) will also have access to unblinded individual participant treatment assignments for the purposes of study-required activities, including management of study drug inventory, production of summaries of data for IDMC review, and performance of bioanalytical analysis. These personnel will not be directly involved in the conduct of the study.

An IDMC will periodically convene to review unblinded overall safety and emerging efficacy results (Section 8.5).

The RTSM system will be programmed with blind-breaking instructions. In case of a medical emergency, the Investigator has the sole responsibility for determining if unblinding of a participant's treatment assignment is warranted. Participant safety must always be the first consideration in making such a determination. The Investigator should notify the Sponsor's Medical Monitor (or designee) prior to unblinding using the RTSM system. The Investigator(s) must document and report to the Medical Monitor any breaking of the treatment code. The date and reason that the blind was broken must be recorded in the source documentation.

Appropriate personnel at the Sponsor (or designee) will unblind suspected unexpected serious adverse reactions (SUSARs) for the purpose of reporting to authorities as required per each local

regulation. The Sponsor will submit SUSARs to Regulatory Agencies in blinded or unblinded fashion according to local law. The Sponsor will submit SUSARs to Investigators in a blinded fashion.

